# **Study Information**

Type of Research: Biomedical Research

# 2) Background/ Key Questions:

In older adults, poor circulation in the lower extremities or dysvascular disease can lead to serious health complications. In addition, these individuals also suffer from serious co-morbidities like diabetes and coronary or cerebrovascular disease. Circulatory dysfunction or dysvascular disease is the major cause for amputations in the United States (www.amputee-coalition.orf/fact\_sheet/amp\_stats\_cause.html). Increasing sedentary lifestyles have lead to increased rates of diabetes which has significantly contributed to an increased number of amputations in recent years. The risk of amputation in a diabetic individual is 25 times higher than in the non-diabetic population (Witsø & Rønningen 2001).

The level of amputation that is appropriate for an individual depends on the extent of damage to his/her tissues. Common amputations of the lower extremities in the dysvascular population include the transtibial and transfemoral amputations. The individual having a transtibial or below knee amputation, will be fitted with a prosthetic foot to assist with functional ambulation, while a person with a transfemoral amputation will require both a prosthetic foot and knee for ambulatory purposes. Currently dysvascular amputees are given prostheses based on the goal of returning them to a basic level of function focused primarily on stability. They are considered lower functioning walkers and are expected to use a slow and constant walking speed to ambulate around their homes and are not considered traditional community ambulators. Therefore, they are traditionally given standard mechanical knees which are considered safe, as they provide the ability for only simple single speed house-hold tasks. While this criterion does return the patient to function for basic Activities of Daily Living (ADLs) and walking at a single cadence, it does not empower the patient to counteract the previously existing comorbidities. Dysvascular amputees tend to be less active predisposing them to a more sedentary lifestyle and exacerbating their risk factors. Their prostheses make them energy inefficient and use more energy for ADLs and functional walking. This causes early onset of fatigue, induces anxiety and fear of falling. Further, they are often depressed, lose motivation and curtail their community interaction. This raises the question if dysvascular amputees are further functionally limited by the prostheses traditionally given to them.

More recently, technology has been used to assist with return to function in the amputee population. Microprocessor (MP) controlled knees are among the technological innovations applied to prostheses to not only return amputees to a basic function, but also with a view to return them to their highest possible function. Over the years, clinical use has shown that traditional knees provide the ability to complete ADLs and basic functions like sit – stand. However, activities like negotiating stairs/steps, walking on uneven ground and self-correction during tripping; functions which reintegrate amputees into unlimited community ambulation and social reintegration require prosthetics which advanced functionality. The Otto Bock C-leg is a MP knee that allows the patient a greater level of control in swing and stance phases of gait. This enables the TF amputee to adjust the requirements of gait during dynamic walking like changing the speed of walking, going up and down stairs and inclines, walking on grass and uneven surfaces and crossing an obstacle. The C-leg has been traditionally given to patients who begin post-amputation rehabilitation at a higher level, but are more expensive than traditionally mechanical knees. In the contrary however, a European study that defined health outcomes in terms of quality-adjusted life year (QALY), indicated that the C-leg showed a QALY gain of €3218 per patient (Brodtkorb et al 2008), makes it still financial viable keeping it mind its price tag.. The purpose of this study is to compare the traditional mechanical knee to the microprocessor knee (C-leg) in the dysvascular population. The study will specifically evaluate the potential of microprocessor knees to improve the quality of life in dysvascular transfemoral amputees. This includes identifying if the Cleg can increase the activity level to be classified at a higher level by the Medicare classification from K2 (lower level ambulators) to K3 (more proficient ambulators), along with increasing their social interaction in the community.

# 3) Hypotheses & Research Objectives and Purpose:

Central Hypothesis: We hypothesize that giving microprocessor knees (C-leg®), will significantly increase everyday function, social interaction, and quality of life in K2 Dysvascular subjects with transfemoral amputation in comparison to a standard mechanical knee (both FDA Class II exempt devices). The study will primarily aim to study the impact of the C-leg on ADLs and community interaction ADLs and function:

Hypothesis 1: We hypothesize that the C-leg will significantly increase every day physical activity measured using GPS tracked activity in K2 Dysvascular subjects in comparison to a mechanical knee.

Hypothesis 2: We hypothesize that the C-leg will significantly increase functional mobility in K2 Dysvascular subjects compared to a mechanical knee: increased stepping measured using Step Activity Monitor (SAM), increased gait speed and distance measured by Six Minute Walk Test (6MWT), increased mobility measured by the Amputee Mobility Predictor (AMP).

Hypothesis 3: We hypothesize that the C-leg will significantly increase community mobility measured using GPS technology in K2 Dysvascular subjects in comparison to a mechanical knee.

# Sub -hypothesis

- 3a: That C-leg will improve ambulation distance vs. mechanical knee
- 3b: That C-leg will improve time out of home vs. mechanical knee
- 3c: That C-leg will improve ability to use public transport vs. mechanical knee
- 3d: That C-leg will decrease gait aid vs. mechanical knee

Hypothesis 4: We hypothesize that the C-leg will significantly improve social integration as measured by CPI (Community Participation Indicators) in K2 Dysvascular subjects in comparison to mechanical knee.

Hypothesis 5: We hypothesize that the C-leg will significantly improve both static and dynamic balance as measured by Single Leg Stance (SLS), Timed Up and Go (TUG), BERG Balance Scale (BBS), Four Square Step test (FSST) and Dual task TUG tests in K2 Dysvascular subjects compared to a mechanical knee.

Hypothesis 6: We hypothesize that the C-leg will significantly improve self-reported measures in K2 Dysvascular subjects in comparison to mechanical knee.reduced falls measured by The Falls Efficacy Scale (FES), improved prosthesis use measured by The Prosthesis Evaluation Questionnaire (PEQ)

This study will be conducted at the Rehabilitation Institute of Chicago, [name].

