# IV. Assess and compare patient perception and preference:

- a. To determine falls and near falls, subjects will fill out a self- reported Falls Efficacy scale (FES)
- b. To determine if cognition is a limitation the Mini-Mental State Exam (MMSE) will be administered.
- c. To determine prosthesis use and preference, the Prosthesis Evaluation Questionnaire (PEQ) will be given to the subject to fill out.
- d. These questionnaires will take between 5-20 minutes each to fill out.

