# **Data Collection and Analysis**

Subjects will be screened and medical history and information relevant to why and when they received an amputation will be accessed from their medical records. Subjects will be explained the study design, procedures, tests, questionnaires and physical therapy visits asked to sign an informed consent prior to participating in the study. After subjects are randomized into two groups, they will be provided with a GPS device and a step activity monitor which will track their walking/mobility patterns at home and in the community for 4 weeks. When they return, over 1-2 visits, they will be assessed for a full battery of baseline outcome measures: six minute walk test (6 mwt), Amputee Mobility Predictor (AMP), Timed Up and GO (TUG), BERG balance test,. They will also be required to fill in self-report questionnaires for falls and the PEQ. They will then be fitted with the randomized prosthesis and new foot by a certified prosthetist. There will a period of acclimation for 3 months during which patients will be provided physical therapy with either the C-leg with a new foot or a mechanical leg with a new foot. Subjects will come for an average of two times a week for physical therapy training. The pre-training visits will include 1 for informed consent and GPS, 1-2 for evaluation and an additional 1-2 for prosthetic fit. The training sessions will be a maximum of 14. There will also be 1-2 reassessment visits. This will be repeated for the other prosthesis. There will be a maximum total of up to 45 visits. Subjects will be compensated \$40 per session for evaluation and assessments, prosthetic fittings and training sessions. This is the usual amount in similar studies and other studies at the Rehabilitation Institute of Chicago. The total compensation will be determined by the number of sessions that the subject completes while enrolled in the study. There will be 2 sessions allowed for a subject to be paid, even if they arrive but are unable to complete a session due to unscheduled issues (such as illness). However, if patients miss 3 or more consecutive visits, or experience a medical illness that may/may not require hospitalization, patients may have to be withdrawn from the study. Patients will be offered the additional service of adjustments for prosthesis/refining home exercise program in phone or in person, but they will not be compensated for these patient initiated services.

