#### Withdrawal criteria

- 3 or more consecutive or 5 total per leg missed sessions
- Hospitalizations
- At PI's discretion for unforeseen/unplanned medical events that may alter inclusion or exclusion criteria

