# Safety Assessment Risk and Injury

The primary risk in this study is the risk of falls, regardless of the prosthesis used. Fall prevention is a primary focus and the risk will be reduced by the use of harnesses, gait belts, assistive devices as needed and stand-by or contact guard assistance and supervision by researchers. All subjects will be initiated with testing and therapy sessions with simple activities, progressing on to more dynamic, complex activities when it is clear that they are safe and acclimated to the prosthesis being used. Other risks include muscle soreness from exercises during therapy sessions. To avoid this, subject will be provided with adequate rest periods and subjects will be monitored by questions regarding discomfort. Skin irritation from adjusting to a new socket fit can also be a risk. This risk will be minimized by regular check ups by a certified prosthetist, who will check for skin lesions/breakdowns.

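### Hypothesis 6 claims fewer falls from a questionnaire alone, and a fall that ends a subject's participation enters no planned measure

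*Combined protocol and SAP*

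**What the plan says.** - **Outcome.** Hypothesis 6 (section 3, under the sub-hypotheses) lists "reduced falls measured by The Falls Efficacy Scale (FES" among the self-reported measures to be compared between knees.
- **Instrument.** Research Methods, part IV: "To determine falls and near falls, subjects will fill out a self- reported Falls Efficacy scale (FES". The FES items are not described, and no diary, log or count of falls appears anywhere.
- **Timing.** Data Collection and Analysis puts a falls questionnaire in the baseline battery: "They will also be required to fill in self-report questionnaires for falls and the PEQ". One or two reassessment visits follow for each prosthesis. The design table schedules monthly collection in all four phases without naming the measures. For the assessment period, the text names only the AMP and the six-minute walk for regular collection.
- **Safety.** "The primary risk in this study is the risk of falls, regardless of the prosthesis used". That section deals with prevention and supervision, not with recording falls.
- **Withdrawal.** The criteria include "3 or more consecutive or 5 total per leg missed sessions" and "Hospitalizations", with no exemption for falls. Data Collection and Analysis is softer: subjects who miss three or more consecutive visits, or who "experience a medical illness that may/may not require hospitalization, patients may have to be withdrawn from the study".
- **Analysis.** A two-way repeated measures ANOVA at two-sided 0.05, with 40 randomised to allow for 30% attrition. No analysis set, missing-data rule or collection after withdrawal is given.

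**The concern.** The event that Hypothesis 6 is about can itself end observation. A fall serious enough to cause an admission or a run of missed sessions comes after the subject's last questionnaire. If the subject is then withdrawn, nothing in the plan captures that fall. No later treatment of missing FES scores can recover it, because it was never written down.

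Two things are at stake. A conclusion that falls were reduced could rest on a score that does not reflect the most serious falls. And the trial would finish without a count, by knee, of the event it names as its main risk.

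**Working it through.** **1. The plan's own attrition figure.** 28 / (1 − 0.30) = 40, so 40 randomised is consistent with 28 completers and 40 × 0.30 = 12 expected losses. The 28 cannot itself be re-derived, because no effect size or standard deviation is given. Nothing below depends on it.

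**2. How easily a fall can trigger withdrawal.** The plan says: "Subjects will come for an average of two times a week for physical therapy training".
- Three consecutive sessions at two a week: 3 / 2 = 1.5 weeks.
- Training is capped at 14 sessions per knee: 14 / 2 = 7 weeks, or 7 / 26 = 27% of the six months on each knee.
- In the assessment period visits are roughly monthly, so three consecutive misses would span months.

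The 1.5-week figure therefore holds only in the training weeks. The hospitalisation criterion applies throughout.

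**3. Effect on a fall-rate ratio.** The documents give no fall rates, so the inputs are assumed. Let pC and pM be the shares of falls on the C-leg and mechanical knee that end participation and go unrecorded. If falls follow a Poisson process within a subject, the recorded falls on knee k have rate λk(1 − pk), so

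recorded ratio = true ratio × (1 − pC) / (1 − pM).

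| pC | pM | Factor |
|---|---|---|
| equal | equal | 1.00 |
| 15% | 5% | 0.85 / 0.95 = 0.89 |
| 5% | 15% | 0.95 / 0.85 = 1.12 |
| 30% | 10% | 0.70 / 0.90 = 0.78 |
| 10% | 30% | 0.90 / 0.70 = 1.29 |

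The last two rows are a deliberate extreme with no basis in the documents.

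**4. What is lost with equal shares.** Assume 1.5 falls per six months on the mechanical knee, a true ratio of 0.60 (0.9 on the C-leg, difference 0.60) and gamma frailty with mean 1 and shape 1. If a share s of falls on either knee ends participation, and nothing else does, the fraction completing is 1 / (1 + 2.4s), where 2.4 = 1.5 + 0.9. The completers' difference in mean falls is 0.60 × (1 − s) / (1 + 2.4s):
- s = 5%: 89% complete; 0.60 × 0.95 / 1.12 = 0.51
- s = 10%: 81% complete; 0.60 × 0.90 / 1.24 = 0.44
- s = 20%: 68% complete; 0.60 × 0.80 / 1.48 = 0.32

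The ratio stays at 0.60 and the absolute difference shrinks.

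**5. Effect on a test at the plan's level.** A crossover was simulated with 40 subjects, six months per knee, about 30% attrition, frailty variance 1, 0.05, 0.10 or 0.15 falls per month and equal shares of 20%. The standard deviation of the log ratio in completers was 0.67, 0.48 and 0.40. With no true difference, a shift of δ in favour of the C-leg makes the chance of a significant result in its favour Φ(−1.96 + δ / SD), against 2.5% without it.
- 15% v 5%: δ = ln(0.95 / 0.85) = 0.111, giving about 3.6%, 4.2% and 4.6%
- 30% v 10%: δ = ln(0.90 / 0.70) = 0.251, giving about 5.7%, 7.5% and 9.2%

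**The case against.** **The figures describe an analysis the plan does not contain.** The plan compares FES responses by ANOVA and never estimates a fall-rate ratio. This stands. The figures in the working show how a falls comparison would behave; they do not measure bias in the FES score.

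**Nothing shows that the shares differ by knee.** A reader might infer that the planned comparison is biased in a known direction, since the Background credits advanced knees with recovery from trips and Hypothesis 3 expects more community walking. Both bear mainly on how often people fall, which leaves the ratio unbiased. No passage says that falls on one knee are more serious. This stands too.

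**Withdrawal is discretionary, and collection is monthly.** Withdrawn subjects may have earlier FES forms. A reader might infer that the plan analyses completers only; that follows from silence about missing data and is not stated. The point does not need it. Even a monthly form would precede the fall that stops the visits, and discretion without a recording rule does not capture that fall.

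**This is one instrument in the last of six hypotheses.** The stated primary aim is daily activities and community interaction. That limits the severity, but it does not supply a falls record for the risk the plan itself puts first.

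**Conclusion.** The point holds in a limited form. Hypothesis 6 rests a claim about falls on a questionnaire alone, and a fall that leads to withdrawal enters no planned measure. That follows from reading the hypothesis, the withdrawal criteria and the collection schedule together, and it needs no assumption about rates.

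The size of any distortion does need assumptions. It is nil on the ratio scale if the shares are equal, and a factor of 0.89 to 1.12 for an assumed 5% v 15%. Even in the extreme case, the chance of a false result favouring the C-leg rises from 2.5% to no more than about 9%. The documents do not support a stronger conclusion that the falls result will be wrong, or wrong in a particular direction. Nor do they support reading 1.5 weeks of absence as a trigger throughout follow-up. This is a minor improvement, worth making because it is cheap.

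**What to change.** 1. Define a fall in one sentence.
2. Log every fall from first fitting of a study knee to end of follow-up or withdrawal, including the fall that leads to withdrawal. Record the date, the knee worn, and whether the fall led to admission or withdrawal. Ask at the existing therapy and monthly contacts, and once by phone at withdrawal.
3. As a supportive estimate, report falls per person-month by knee in all fitted subjects. Give a rate ratio and 95% interval from a count model (for example negative binomial) with knee, period, a person-time offset and a subject effect.
4. Beside it, give counts by knee of falls leading to admission or withdrawal, and all withdrawals by knee and reason.
5. Keep the FES, but report it as a questionnaire score and not as reduced falls. The withdrawal criteria stay as they are.

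**Cost.** A short log, one question at existing contacts, one call at withdrawal, and software beyond StatView 5.0.1, the only package the plan names. No new visits or subjects.

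**Limits.** Falls rely on recall, and falls after withdrawal are not counted. The interval will be wide. In the same simulation, with all fitted subjects counted and no period effect simulated, the standard deviation of the log ratio was 0.53, 0.36 and 0.30. The 95% limits then lie a factor of exp(1.96 × SD) = 2.8, 2.0 and 1.8 either side of the estimate, so a moderate reduction might not be confirmed.

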# 4) Research Methods: Study Design:

The study will have a randomized, repeated measures design. Due to the high rate of attrition we will randomize a total of 40 subjects, 20 into each of the groups below.

Group I

Mech Knee+Old Foot	C-leg + New Foot	C-Leg + New Foot	Mech knee + New Foot	Mech knee + New Foot
>6 months post TF prosthetic fitting	Acclimation	Assessment	Acclimation	Assessment
Duration	3 months	3 months	3 months	3 months
Data Collection	Monthly	Monthly	Monthly	Monthly

Group II

Mech Knee+Old Foot	Mech Knee + New Foot	Mech Knee +New Foot	C-Leg+ New Foot	C-Leg+ New Foot
>6 months post TF prosthetic fitting	Acclimation	Assessment	Acclimation	Assessment
Duration	3 months	3 months	3 months	3 months
Data Collection	Monthly	Monthly	Monthly	Monthly

All measures will be administered and data collected under the supervision of a licensed physical therapist.

- I. Assess and compare mobility in TF amputees:
  - a. To quantify community ambulation including time spent out of the home, use of public transport, GPS technology will be used. Subjects will be required to wear a GPS monitor on their belts during the day. This will track their activities in their homes and in the community.
  - b. To assess functional mobility the Amputee Mobility Predictor will be used. A standardized sequence of mobility tests with the prosthesis will be administered on the first pre-acclimation session. The patient will be scored out of 39.
  - c. To quantify fall risk and functional mobility the Timed Up and Go (TUG) test will be used. TUG is the time taken for the subject to get up from chair, walk 3 meters and sits down; measured in seconds.
  - d. To objectify the amount of steps in ADLs and functional mobility the Step Activity Monitor will be used. The subject will be given a monitor that he/she will have to wear around his/her ankle. This will record the number of steps.
  - e. To determine community and social participation, the Community Participation Indicators questionnaire will be used. It is a valid, new generation of self-report outcome measure for community participation. It will take 15-30 minutes to complete and will be administered in room 1771.
- II. Assess and compare gait distance and speed:
  - a. To determine maximum gait distance while using the prosthesis, distance and perception ratings will be recorded during the 6 minute walk test. Subjects will walk for 6 minutes with prosthesis with researcher walking alongside with walking wheel to determine distance walked in 6 minutes while recording their Rating of Perceived Exertion on the Borg Scale.

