The training will focus on providing both groups 1) strength training for upper limbs, core and lower limbs, 2) functional training, e.g. sit – stand, gait training on level surfaces, community ambulation and 3) cardiovascular and endurance training. The following 3 months there will be an assessment period for that particular knee and foot combination. In the course of the assessment period, patients will come in at regular intervals for data collection for the AMP and the 6 mwt. During the last 2 weeks of the assessment, patients will be given GPS devices for tracking their mobility data. At the end of 6 months there will be a crossover where patients with the mechanical leg will receive a new C leg + new foot and patients with the C leg will receive a mechanical leg + new foot. Once again, this will be followed by baseline testing, a period of 3 months acclimation with physical therapy sessions and a 3 month period of assessment where patients will come in for data collection. In the last 2 weeks, GPS data will be collected. The data collected will be analyzed for differences in outcome measures caused by the different prosthetic devices.

During the data collection process and the training sessions, a licensed physical therapist will be present to provide supervision and monitoring of the patient's vitals, signs and symptoms. During the sessions, subjects may be photographed or videotaped performing assessments, functional tasks, or exercising, with their consent. The photos and video recordings will not include the subjects face and if used for presentations or publications, will not identify the subject. The data collection and the training sessions will be terminated if the subjects expresses that he/she is unable/does not wish to participate. Subjects will be compensated \$40 per session. Payment will be in cash or by ClinCard per session, at the end of each session. RIC is moving away from using petty cash. During this transition period the subject may be paid in cash or by ClinCard. If a ClinCard is available when you come for the the study, you will be paid by card. If a ClinCard is not available, then you will receive cash payments.

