If the subject is issued a ClinCard, which is a specially designed debit card for clinical research, the funds will be loaded as appropriate. When a visit is completed, funds will be approved and loaded onto the card. The funds will be available within 1 day after being loaded and can be used at the subject's discretion. The subject will be issued one card for the duration of your participation. If your card is lost or stolen, please call [contact] or ask a coordinator for a replacement ClinCard.

Fees are incurred if used at an ATM (fees vary by location). However, if the card is used for in-store or online purchases via credit or debit, or presented to a bank teller, there are no associated fees and no expiration date.

If subjects wish to join RIC's gym to exercise to increasing endurance and fitness, we will provide them membership (with an RIC physician signing membership form) to RIC's Fitness Center and Sports Program (a \$35 cost that the study will pay to the Fitness Center for the subject). Subjects may be required to participate in a maximum of 45 sessions, although the maximum may not be needed for all subjects. The maximum

compensation is \$1800, although the total compensation will be determined by the number of sessions that the subject completes while enrolled in the study.

The data collected will be analyzed offline. All data and medical information of potential subjects will be locked in a file cabinet in the office of the PI. All study personnel listed will have access to the data and medical information. Subjects will be assigned a code when they are enrolled in the study. All GPS data will be analyzed by a researcher who is blinded to the subjects' identity. All data will be kept on computer hard-drives with accounts and passwords for security. Data will be stored in a locked file cabinet and on a secured-access computer. Data will not be destroyed. Only authorized individuals working directly in the study will have access to the computers.

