# 5) Anticipated Results & Potential Pitfalls

We anticipate the dysvascular amputees when using the c-leg will significantly improve in their functional outcomes, increase their community mobility leading in significant health benefits. We do not foresee any potential pitfalls.

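### The six-minute walk has a researcher who can see the knee walking beside the subject, with no fixed script, so a Hypothesis 2 distance endpoint is open to tester influence that the crossover would not cancel.

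*Combined protocol and SAP*

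**What the plan says.** Item II.a of the Study Design section gives the aim of the test: "To determine maximum gait distance while using the prosthesis, distance and perception ratings will be recorded during the 6 minute walk test". The procedure follows: "Subjects will walk for 6 minutes with prosthesis with researcher walking alongside with walking wheel to determine distance walked in 6 minutes", and the sentence ends "while recording their Rating of Perceived Exertion on the Borg Scale". Hypothesis 2 in section 3 names gait speed and distance on this test as outcomes. Data Collection and Analysis puts the 6MWT in the baseline battery. It also names the 6MWT, with the Amputee Mobility Predictor (AMP), as the tests repeated through each assessment period.

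On who tests, the Study Design section says: "All measures will be administered and data collected under the supervision of a licensed physical therapist". Data Collection and Analysis adds: "During the data collection process and the training sessions, a licensed physical therapist will be present to provide supervision". That sentence goes on to the monitoring of vital signs and symptoms, so it describes oversight for safety.

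The only blinding statement in the document is "All GPS data will be analyzed by a researcher who is blinded to the subjects' identity". It covers GPS data and subject identity; it does not cover the 6MWT or the knee.

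Section 5 records the team's expectation: "We anticipate the dysvascular amputees when using the c-leg will significantly improve in their functional outcomes".

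**The concern.** A test of the greatest distance a person can cover in six minutes depends on effort, and effort can respond to the people present. Here one of them stays beside the subject throughout, can see the knee and belongs to a team that expects the C-leg to do better. The plan gives no standard wording, no limit on encouragement and no statement that the subject sets the pace. For the AMP, by contrast, item I.b calls for a standardised sequence.

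At stake is whether a difference in distance between knees can be attributed to the knee. A tester who is a little more encouraging, or walks a little faster, when the subject wears the C-leg would produce a difference that looks like a device effect. This could happen without intent, and it could recur at each repeat of the test.

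**Working it through.** The plan gives no figure on this point. The check therefore has three steps: what the text leaves open, whether the design would remove a tester effect, and whether its size can be found.

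**1. What the text leaves open.** That the tester is unmasked is an inference, but a short one: no masking is stated, and the researcher walks next to a subject who is wearing the knee. That pace or encouragement could vary with the knee is a possibility. The text neither provides for it nor prevents it.

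**2. Whether the crossover removes it.** Let τ be the true C-leg minus mechanical difference, b a tester effect that is present when the C-leg is worn, and π1 and π2 the period effects. Assume no carry-over. The expected within-subject differences, C-leg minus mechanical, are:

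- Group I (C-leg first): τ + b + (π1 − π2)
- Group II (C-leg second): τ + b + (π2 − π1)
- Average of the two groups: τ + b

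The period effects cancel and b does not. The Statistical Analysis section plans a two-way repeated measures ANOVA with prosthesis and testing session as factors. Its prosthesis effect estimates τ + b, and no term in the model separates the two.

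**3. Size.** The document gives no value for b, no standard deviation (SD) for 6MWT distance and no effect size behind the sample size. The one usable input is the sample size: 40 randomised with 30% attrition, so 40 × (1 − 0.30) = 28 completers (and 28 / 0.70 = 40 returns the stated figure). How 28 was reached cannot be reproduced.

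The table shows only how sensitive the comparison would be. Every value of b is an assumption. It takes τ = 0, b in SDs of the within-subject difference, a two-sided 0.05 level and a paired t test standing in for the ANOVA. The chance of a significant result favouring the C-leg is P(T > t0.975, n−1), where T is noncentral t with noncentrality b√n. For example, n = 28 and b = 0.2 give 0.2 × √28 = 1.06 and a chance of 17.4%.

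| Assumed b (SD) | 28 completers | 40 completers |
|---|---|---|
| 0 | 2.5% | 2.5% |
| 0.1 | 7.4% | 9.0% |
| 0.2 | 17.4% | 23.4% |
| 0.3 | 33.4% | 45.6% |
| 0.5 | 72.3% | 86.9% |

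More completers make the problem worse, because a fixed bias is then detected more reliably. The table does not say which row applies.

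**The case against.** The strongest reply is that the text gives an innocent reason for the researcher's position: measuring the distance. A wheel operator can match the subject's speed. Wheel-measured distance needs less judgement than Berg or AMP scoring, the 6MWT is not designated primary, and the lack of stated masking applies to every performance test. All of this is fair. It limits the point to an avoidable weakness in one procedure, but it does not supply the missing script or show that the position is neutral.

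A reader might go further in four ways that the document does not support:

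- **That the researcher paces the subject, or that anyone alongside must do so.** Nothing in the text says this. Section 5 shows an expectation, not an altered distance.
- **That the tester is the therapist who trained the subject.** Item II.a says researcher, and the sentence on the therapist's presence concerns safety oversight. Overlap is not excluded, but it is conjecture.
- **That the wheel biases the result because it records the operator's path.** That error occurs on both knees, with no stated reason to favour either.
- **That the bias can be put in metres.** This would need a walking speed and a pacing effect, both invented.

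The other side is also right about remedies. The Safety Assessment section names falls as the primary risk and provides for close guarding, so a measurement change should not prescribe where a guarding person stands. Barring a therapist from testing on the knee that he or she trained could also give one subject different testers on the two knees. Between-tester differences would then enter the within-subject comparison.

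**Conclusion.** The point holds as a cheap improvement to a stated procedure. The 6MWT set-up leaves pace and encouragement open to influence by someone who can see the knee. Any influence that followed the knee would pass undiminished into the Hypothesis 2 comparison. The direction that team expectation would favour is the C-leg; whether any bias would occur, and how large it would be, cannot be derived from the document.

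The conclusion rests on two inferences: that the researcher can see the knee, and that distance in a maximum-effort walk can respond to the tester. The cancellation result also assumes no carry-over. The percentages in the table depend wholly on assumed values of b and are not an estimate for this trial.

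**What to change.** In item II.a, replace the instruction to walk beside the subject with one of two procedures: the wheel operator trails behind the subject, or laps are counted on a measured course. Add one identical script with fixed phrases at fixed times, including the Borg prompt and who gives it. Apply it on both knees, at every visit, to everyone present.

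Leave the guarding and supervision in the Safety Assessment section unchanged. Where possible, keep the same tester for a given subject on both knees.

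State unmasked assessment as a limitation, since the script and position reduce tester influence but do not remove it. Name the Step Activity Monitor counts, also a Hypothesis 2 outcome, as a device-recorded consistency check. They measure daily stepping, not maximum distance, so agreement would support the 6MWT result but disagreement would not by itself show bias. The check needs monitor data on each knee. Data Collection and Analysis names the monitor only for the four weeks before fitting, and only GPS for the last two weeks of each assessment period, so the plan should state when the monitor is worn on each knee.

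The cost is a few sentences, a little tester training and a slightly less convenient procedure. Sample size and visit numbers need not change.
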